6.3.2 Visit 2: Period 1 Mid-Treatment Evaluation (Day 10)

- Subjects will report to the [REDACTED] facility for study procedures
- Dental Examiner will complete a dental examination and record any AEs, as required
- Dental photographs may be taken by study staff if oral tissue sloughing or irritation are found at the dental exam of the affected areas
- Study Coordinator will schedule follow-up visit(s)

6.3.3 Visit 3: Period 1 End of Treatment (Day 21)

- Subjects will report to the [REDACTED] facility for study procedures
- Subjects will return completed subject diaries, study toothpaste tubes, and 3M Oral Rinse bottles.
- Dental Examiner will complete a dental examination, review subject diary, and record any AEs, as required
- Dental photographs may be taken by study staff if oral tissue sloughing or irritation are found at the dental exam of the affected areas
- Subjects will complete the questionnaire
- Study Coordinator will dispense the assigned toothpaste for at least a 1-week washout
- Study Coordinator will schedule follow-up visit(s)

6.3.4 Visit 4: Period 2 Baseline (Day 28+)

[figure not shown]
- Subjects will report to the [REDACTED] for study procedures
- Subjects will return study toothpaste tubes used in washout
- Dental Examiner will complete a dental examination and record any AEs, as required
- Dental photographs may be taken by study staff if oral tissue sloughing or irritation are found at the dental exam of the affected areas
- Study Coordinator will dispense the assigned toothpaste, 3M Oral Rinse, and subject diary
- Study Coordinator will provide verbal and written product use and subject diary instructions, as needed
- Subjects will initiate their treatment in the evening of baseline visit
- Study Coordinator will schedule follow-up visit(s)

6.3.5 Visit 5: Period 2 Mid-Treatment (Day 38+)

- Subjects will report to the [REDACTED] for study procedures
- Dental Examiner will complete a dental examination, review subject diary and record any AEs, as required
- Dental photographs may be taken by study staff if oral tissue sloughing or irritation are found at the dental exam of the affected areas
- Study Coordinator will schedule follow-up visit(s)

6.3.6 Visit 6: Period 2 End of Treatment / End of Study (Day 49+)

- Subjects will report to the [REDACTED] for study procedures
- Subjects will return completed subject diaries, study toothpaste tubes and 3M Oral Rinse bottles.
- Dental Examiner will complete a dental examination, review subject diary and record any AEs, as required
- Dental photographs may be taken by study staff if oral tissue sloughing or irritation are found at the dental exam of the affected areas
- Subjects will complete the questionnaire

6.4 Assessments

6.4.1 Dental Exam

All dental examinations will be completed by the Dental Examiner. The dental examinations will be documented on study CRFs. The dental examination will include a visual sloughing evaluation divided into 12 assessment areas: dorsal surface of the tongue, ventral surface of the tongue, floor of the mouth, roof of the mouth, right buccal mucosa, gingival tissue (upper right, upper anterior, upper left), left buccal mucosa, gingival tissue (lower left, lower anterior, lower right). The Dental Examiner will evaluate the severity of sloughing in these individual locations using the

the Oral Mucosal Sloughing Index¹.

6.4.2 Subject Diary

All subjects will record compliance to study toothpaste and 3M Oral Rinse and any adverse events experienced on the subject diary, as provided on study CRFs.

6.4.3 Subject Questionnaire

[figure not shown]
All subjects will complete an acceptability questionnaire at the required timepoints, as provided on study CRFs.

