Study Title: **3M Oral Rinse incidence and patient acceptance of sloughing when used with Sodium Lauryl Sulfate (SLS) toothpastes**

NCT Number: **NCT04601103**

Issue Date: **01/07/2020**

1.0 3M Sponsored **Clinical Study** **Summary**

Study #	IRB Number	Project #	Request Date	Date Samples Available	Date Results Needed
[REDACTED]	[REDACTED]	[REDACTED]	15-Oct-2019	11-Oct-2019	15-Apr-2020

[figure not shown]
Study Title:	3M Oral Rinse incidence and patient acceptance of sloughing when used with Sodium Lauryl Sulfate (SLS) toothpastes
Objective:	
The primary objective of this study is to evaluate the incidence of oral tissue sloughing through self-report by study subjects and by professional dental examinations. Adverse events will be tracked through study dental examinations and subject diaries with twice daily use of the 3M Oral Rinse used in combination with toothpaste containing one of three levels (no, medium, high) of Sodium Lauryl Sulfate (SLS).
 
Determine the subjects' acceptance of sloughing and/or other side effects.

	Name	Title	Address	Phone #
Requestor:	[REDACTED]	Commercialization Manager	[REDACTED]	
Principal Investigator:	[REDACTED]	Clinical Affairs Manager	[REDACTED]	
Primary Study Contact:	[REDACTED]	Clinical Project Manager	[REDACTED]	
Staff Dentist:	[REDACTED]	3M Oral Care Staff Dentist	[REDACTED]	

[figure not shown]
Study Will be Used For:		Safety
		Screening

Statistical Analysis Requested:		Yes
		No

Test Assessments		Additional Description
	Adverse Event (AE) incidence rate(s)	Subject reported incidence of adverse events (AEs) on subject diaries and observed during study dental exams.
	Oral Mucosal Sloughing Index	Sloughing severity and location will be captured on study case report forms (CRFs).
	Subject acceptability of sloughing	Subjects will be given a questionnaire on the acceptability of the sloughing and/or other side effects and the use of the 3M Oral Rinse in combination with the assigned toothpaste.

Time Points for Study Procedures		Additional Details

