4.5 Subject Restrictions

Emergency treatment for a broken tooth, lost filling, or crown is permitted during the study, at the discretion of the Investigator.

Subjects that need to be withdrawn from treatment during Period 1 are allowed to enter washout early and complete a longer washout until Period 2.

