4.6 Subject Withdrawal

Subjects may voluntarily withdraw from the study at any time without prejudice.

Any subject may be withdrawn by the Investigator from further participation in the study if the subject:

[figure not shown]
- Fails to adhere adequately to the protocol requirements within or outside the clinical environment
- Fails to cooperate adequately with the Investigator or staff during clinical visits
- Presents with an illness or disease condition that is not allowed in the study
- Experiences a serious AE that requires discontinuation or withdrawal from the study
- Experiences an intolerable AE
- Found not to meet the original entry requirements
- Fails to return for an appointment(s)
- Is pregnant

If a subject discontinues due to an AE (reported by the subject or the Investigator), the causative condition will be followed until resolution or stabilization to the Investigator's satisfaction.

Withdrawn subjects will not be replaced.

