9.4.2 Secondary Analyses

The 95% confidence intervals will be computed for the sloughing rates for each treatment group using the Wilson score method. Significant trends in incidence rates across the treatment groups (from high to medium to no SLS toothpaste) will be tested using the Cochran Armitage test.

The oral mucosal sloughing index score will be used to compute the following two outcomes: (a) Overall subject-level incidence based on any non-zero score among the 12 oral areas examined, and (b) an average subject-level score based on the mean of 12 severity scores over all oral areas for each subject. These outcome scores will be summarized for each treatment group and if appropriate, will be analyzed using a generalized linear regression model such as a Poisson model to test for significant treatment, period and sequence effects.

The diary data will be used to compute treatment compliance with expected number of doses, and this will be summarized per period and treatment group.

Exploratory analysis may occur to examine the onset time and duration of adverse events.

The data collected on the subject acceptance questionnaire will be summarized by treatment group. If appropriate, these data will be analyzed for treatment differences using a generalized linear regression model such as an ordinal logistical model that takes into account the cross over design and the ordinal nature of the data.

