9.6 Procedures for Missing, Unused, or Spurious Data

Missing data due to subject withdrawals or subjects lost to follow-up will not be imputed. All data collected from each subject will be used in the statistical analyses.

[figure not shown]

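### No acceptance questionnaire is scheduled when treatment stops early, so if subjects stop because of sloughing, the acceptance summary will look too favourable

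*Combined protocol and SAP*

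**What the plan says.** The Objective entry in section 1.0 includes: "Determine the subjects' acceptance of sloughing and/or other side effects". Sections 2.0 and 3.1 repeat that aim. Section 6.4.3 says "All subjects will complete an acceptability questionnaire at the required timepoints, as provided on study CRFs". The schedule in 6.2 marks the questionnaire at Visit 3 (Day 21) and Visit 6 (Day 49+) and nowhere else. The visit lists in 6.3.3 and 6.3.6 agree ("Subjects will complete the questionnaire"). No section describes an early-termination visit or a questionnaire on stopping.

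The plan expects some subjects to stop. Section 4.6 lists "Experiences an intolerable AE" as a reason for withdrawal and adds "Withdrawn subjects will not be replaced". For Period 1, section 4.5 states: "Subjects that need to be withdrawn from treatment during Period 1 are allowed to enter washout early and complete a longer washout until Period 2". There is no counterpart for Period 2.

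For the analysis, 9.4.2 says "The data collected on the subject acceptance questionnaire will be summarized by treatment group", with an ordinal model only if judged appropriate. Section 9.6 says "Missing data due to subject withdrawals or subjects lost to follow-up will not be imputed", and that all data collected will be used. Section 9.3 defines no sensitivity analyses.

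**The concern.** A subject who stops because sloughing is intolerable has answered the acceptance question as clearly as anyone can. If that subject leaves before Visit 3 or Visit 6, the answer does not enter the acceptance summary. The chance of being missing then depends on the unseen answer itself, so an ordinal model fitted to the collected questionnaires does not remove the bias. Read as planned, the summary would describe people who tolerated three weeks of use.

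Period 1 stoppers who stay under 4.5 raise a different problem, of timing. If they attend Visit 3 on its scheduled day, they answer from recall, off the rinse and using washout toothpaste A.

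The loss may also be uneven. The only rule that keeps a stopper in the study applies to Period 1, which holds every exposure to A but only part of those to B and C. The comparison between toothpastes could therefore be distorted as well as the overall level.

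**Working it through.** **The plan's own figures.** Section 9.2 gives no figure for acceptance; its precision and power figures are for sloughing incidence. They serve only as a yardstick. The half-width 1.96 × √(p(1−p)/n) with n = 72 gives 11.3 points at p = 40% and 11.5 at p = 50%, as stated. At p = 10% the same formula gives 1.96 × √(0.10 × 0.90/72) = 6.9 points.

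**Exposures by period** (sequence table in 3.1; counts in 8.1, with 24 subjects per sequence).

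| Toothpaste | Period 1 | Period 2 | Share outside the 4.5 rule |
|---|---|---|---|
| A | 24 | 0 | 0/24 = 0% |
| B | 24 | 24 | 24/48 = 50% |
| C | 24 | 48 | 48/72 = 67% |

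**Illustration for C.** Assumptions, none of them in the documents: k of the 72 exposures end in a stop because the product is unacceptable; 10% of the other 72 − k subjects answer unacceptable; stops are spread evenly, so k × 24/72 = k/3 fall in Period 1.

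- All stoppers lost: 0.10(72 − k)/(72 − k) = 10% for any k.
- Period 1 stoppers still answer at Visit 3, and answer unacceptable: [0.10(72 − k) + k/3]/[(72 − k) + k/3].
- Everyone counted: [0.10(72 − k) + k]/72.

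For k = 6 these are 6.6/66 = 10.0%, (6.6 + 2)/(66 + 2) = 8.6/68 = 12.6%, and (6.6 + 6)/72 = 12.6/72 = 17.5%.

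| k | All lost | Period 1 stoppers answer | Everyone counted | Shortfall (points) |
|---|---|---|---|---|
| 0 | 10.0% | 10.0% | 10.0% | 0 |
| 3 | 10.0% | 7.9/70 = 11.3% | 9.9/72 = 13.8% | 2.5 to 3.8 |
| 6 | 10.0% | 8.6/68 = 12.6% | 12.6/72 = 17.5% | 4.9 to 7.5 |
| 10 | 10.0% | 9.53/65.33 = 14.6% | 16.2/72 = 22.5% | 7.9 to 12.5 |

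**Illustration for A against C.** Assume true acceptance of 90% on A with no stops, and 70% on C with 10% stopping, all of them non-accepters. The true gap is 20 points. If every C stopper is lost, C reads 0.70/0.90 = 77.8% and the gap 12.2 points. If only the Period 2 two-thirds are lost, C reads 0.70/(1 − 0.0667) = 75.0% and the gap 15.0 points.

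**Timing for Period 1 stoppers who stay.** If Visit 3 is held on Day 21, the time off assigned treatment is 21 − stop day. A stop on Day 14 gives 7 days, equal to the protocol's minimum washout; earlier stops give more.

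**The case against.** Four points can be made on the other side.

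- A reader might infer that no stopper ever completes the questionnaire for the toothpaste that caused the stop. The documents do not support that. A Period 1 stopper kept under 4.5 is still in the study, nothing cancels Visit 3, and 6.4.3 speaks of all subjects. Whether Visit 3 is kept on Day 21, brought forward or skipped is not stated. For these subjects the defect is unclear timing; certain loss applies only to those who leave without reaching the questionnaire visit.
- A reader might also infer that anyone stopping in Period 2 simply leaves. Section 4.5 is silent on Period 2. Section 4.6 makes withdrawal a discretion of the investigator and requires follow-up of an adverse event that led to discontinuation. Contact continues, so the answer could be obtained; the plan just does not ask for it.
- No stop rate is given, and 5.2 anticipates mild, transient sloughing. Stops may be few. This stands: the size is unknown, and the tables above are illustrations.
- Acceptance is analysed as a secondary outcome, and the primary endpoint in 9.4.1 does not use the questionnaire. Diaries and examinations still record sloughing as an adverse event. This also stands and limits the point to the acceptance objective.

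None of this supplies a rule for collecting the questionnaire at a stop, or an analysis showing what its absence does.

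**Conclusion.** The gap holds and is worth closing as a cheap improvement. The questionnaire timing, the foreseen stops, and the absence of imputation and sensitivity analysis are all in the text. If subjects leave because of sloughing, the direction of bias is toward acceptable. With 6 of 72 stops on C and the assumptions above, the unacceptable share is understated by about 4.9 to 7.5 points, similar to the 6.9-point sampling half-width at 10%. With no stops it is zero.

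Two further readings go too far. That the loss rises with SLS level is a possibility: it rests on the Period 1-only retention rule and the trial's own hypothesis in 9.1, not on data. And a Day 21 examination a week or more after stopping cannot be called fully washed out. One week is the protocol's minimum washout, not a statement that sloughing has cleared by then. Such an examination is off treatment, and no more than that can be said.

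**What to change.** In 6.2, 6.3 and 4.5/4.6, state that a subject who stops assigned treatment in either period completes the existing end-of-treatment questionnaire and returns the diary at the stopping contact, by phone or e-mail if the subject will not attend. If the subject attends, the end-of-treatment dental examination is done then. This concerns data collection only and need not settle when washout toothpaste starts.

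In 9.4.2, report questionnaire completion and the number stopping for oral adverse events, by toothpaste and period, beside the acceptance summary. Add a sensitivity analysis that counts a subject who stopped for sloughing or another oral side effect and left no questionnaire as not accepting that toothpaste-rinse combination; amend 9.3 to allow it. This belongs in a sensitivity analysis and not in the main summary: it is a single imputation, the response scale is not shown in the documents, and stopping for another oral side effect is not necessarily a rejection of sloughing.

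The cost is a short amendment, a little extra contact for a few subjects, and possibly a less favourable acceptance figure.

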7.0 Adverse Events

According to the FDA Guidance (Guidance for Clinical Investigators, Sponsors, and IRBs, Adverse Event Reporting to IRBs-Improving Human Subject Protection-2009), an Adverse Event (AE) can be any unfavorable and/or unintended sign, symptom, or disease temporally associated with the use of an investigational product, whether or not it's related to the investigational product.

AEs can range from anticipated to unanticipated and from mild to serious in nature. Any AE observed during the conduct of a study should be tracked on the AE CRFs, even if they are anticipated and mild. However, while we track these events/side effects, most of these occurrences do not meet the criteria for IRB notification.

Of greater concern are those AEs considered to be unexpected and/or serious in nature and could have implications for human safety. A serious adverse event is defined as any untoward medical or dental occurrence that, at any dose: 1) results in death, 2) is life-threatening, 3) requires inpatient

hospitalization, 4) results in persistent or significant disability/incapacity, or, 5) in a congenital anomaly/birth defect. AEs of this nature are required to be reported.

For this study, an adverse event record will be completed and reported to the 3M IRB within 48 hours for any observation of:

- Any occurrence of an unanticipated adverse event,
- Anticipated AEs that occur at a higher frequency or severity that is inconsistent with prior observations,
- Any occurrence that results in a medical or dental consultation, or,
- Any occurrence of a serious adverse event

[figure not shown]
In addition, an adverse record will be completed and will be included in the final report for the following anticipated observations of:

- Temporary, mild, mouth or tongue sensations such as:
 - Numbness,
 - Mild taste alteration,
- Mild dry mouth,
- Mild superficial tissue sloughing.

The study Principal Investigator (PI) will monitor all adverse incidents and will triage any subject who experiences either an unintended and/or serious AE and determine the course of action (i.e. if they need to be seen by a dental or medical professional). If a dental consultation is necessary the PI/Study Coordinator will contact the 3M Staff [REDACTED] [REDACTED] If medical care is necessary, the subject will be directed to the [REDACTED]

At the subject's request, they may be referred to another health care professional. In the event of a research-related injury, compensation will be determined on a case-by-case basis.

A written report of all unanticipated and/or serious AEs will be submitted to the 3M IRB office within 48 hours of the Investigator's knowledge of the event. The 3M IRB may require additional reports until the event is resolved. Reports for all Serious Adverse Events (SAEs) and Adverse Device Reaction (ADRs) will also be forwarded to the [REDACTED] department for FDA

notification as appropriate. The final study report will include a comprehensive listing of all AEs; anticipated, unanticipated, and from mild to serious in nature.

8.0 Randomization

8.1 Randomization

Subjects will be numbered from 01 through 72. This number will be used to identify the subject on the case report forms. Subjects will be randomized in a 1:1:1 ratio into three different two-treatment sequences: (1) A-> C (2) B->C and (3) C->B. All seventy-two (72) subjects will be exposed to the high SLS toothpaste (C), 48 subjects will be exposed to the medium SLS toothpaste (B), and 24 subjects will be exposed to the no SLS toothpaste (A). See Appendix II for the randomization schedule.

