3.0 Study Plan

3.1 Design

This will be a single-blind, randomized, internal, two-period crossover 3M sponsored study evaluating the incidence of sloughing over time with 3 levels (high, medium, no) of sodium lauryl sulfate (SLS) toothpaste in combination with the 3M Oral Rinse. In addition, this study is designed to determine the acceptance of sloughing and other side effects of using the 3M Oral Rinse in combination with the assigned toothpaste.

Each subject will be assigned to use the 3M Oral Rinse and randomized to one of three toothpaste sequences. Each sequence will consist of using two different fluoride toothpastes (Toothpaste A, B or C), as shown in the table below. The cumulative duration of dosing with 3M Oral Rinse will be six (6) weeks (two 3-week periods). There will be a wash-out period of at least one week between each period.

[REDACTED]

Sequence: Period 1 → Washout → Period 2

	Period 1 (3 weeks)	Period 2 (3 weeks)
Sequence 1	No SLS (Toothpaste A)	High SLS (Toothpaste C)
Sequence 2	Medium SLS (Toothpaste B)	High SLS (Toothpaste C)
Sequence 3	High SLS (Toothpaste C)	Medium SLS (Toothpaste B)

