5.0 Study Materials

5.1 Description

- 3M Oral Rinse: The principle components of the 3M Oral Rinse being used in this study are described in Section 1.0 of this document and are the same for all treatment arms being used in this study. 15mL of 3M Oral Rinse will be swished for about 30 seconds twice a day (morning and evening), after brushing teeth with assigned toothpaste, for each 3-week treatment arm.

- Treatment A consists of a no SLS containing toothpaste. For the study, subjects randomized to Treatment A will receive 1 tube of Sensodyne ProNamel Fresh Breath toothpaste. The information on the components of Sensodyne toothpaste are listed on the packaging and safety data sheet.
- Treatment B consists of a medium SLS containing toothpaste. For the study, subjects randomized to Treatment B will receive 1 tube of 3M ESPE Clinpro Tooth Creme toothpaste. The information on the components of 3M Clinpro toothpaste are listed on the packaging and safety data sheet.
- Treatment C consists of a high SLS containing toothpaste. For the study, subjects randomized to Treatment C will receive 1 tube of Colgate Cavity Protection toothpaste. The information on the components of Colgate toothpaste are listed on the packaging and safety data sheet.

Subjects will be randomized to take two treatment products in sequence: either A followed by C, B followed by C, or C followed by B. Each of the treatments will be used in combination with the 3M Oral Rinse.

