9.0 Data Analysis

9.1 Statistical Hypothesis

[figure not shown]
The main hypothesis under investigation is that the incidence of sloughing over a 3-week period will be positively correlated with the level of SLS in the toothpaste assigned.

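### Toothpaste A appears only in Period 1 and the Period 2 share rises with SLS level, so SLS level is partly confounded with period; adding a C-to-A sequence balances this with the same 72 subjects

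*Combined protocol and SAP*

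**What the plan says.** Section 3.1 describes a "single-blind, randomized, internal, two-period crossover 3M sponsored study". Section 8.1 sets the allocation: "Subjects will be randomized in a 1:1:1 ratio into three different two-treatment sequences". Section 5.1 gives the permitted orders: "either A followed by C, B followed by C, or C followed by B". The schedule in Appendix II matches, with 24 subjects in each sequence. No sequence places A in Period 2, and no reason is given.

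The main hypothesis (Section 9.1) is that "the incidence of sloughing over a 3-week period will be positively correlated with the level of SLS in the toothpaste assigned".

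The primary analysis (Section 9.4.1) is a logistic model with a random subject effect and fixed treatment, period, sequence and treatment-by-period terms. If it does not converge, Fisher's exact test may be used on all data; if the interaction is significant, on Period I only. Section 9.4.2 gives Wilson intervals per toothpaste, and the ordered trend "will be tested using the Cochran Armitage test". Section 9.4.3 applies overall and pairwise Fisher tests to adverse events. None of these fallback, secondary or adverse-event methods includes a period term.

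**The concern.** The share of exposures falling in Period 2 rises with SLS level, in the same direction as the hypothesis. Anything that changes sloughing or its reporting between periods can then look like an SLS gradient, or hide one.

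The protocol makes a period effect plausible. Subjects are not blinded (Section 8.2) and their own reports count toward the primary endpoint (Section 9.4.1), so noticing and reporting may change with experience. Rinse exposure accumulates over two periods. Period 2 follows at least a week on toothpaste A without rinse, whereas no run-in precedes Period 1.

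At stake is the no-SLS reference. It has the fewest exposures, and the Cochran-Armitage test that depends on it is the only named test of ordered trend.

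**Working it through.** **Plan's own figures.** Section 9.2 states 74% power (50% vs 25%, 72 vs 48) and 77% (25% vs 1%, 48 vs 24) for a two-sided Fisher test at 0.05. Exact enumeration, with the two-sided p as twice the smaller tail, gives 74.2% and 77.6%. Both reproduce. They depend only on exposure counts, so reordering sequences leaves them unchanged.

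**Counts** (Section 8.1, Appendix II; the balanced layout is 12 A-C, 12 C-A, 24 B-C, 24 C-B):

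| Toothpaste | Current P1 / P2 | Period 2 share | Balanced P1 / P2 |
|---|---|---|---|
| A | 24 / 0 | 0% | 12 / 12 |
| B | 24 / 24 | 50% | 24 / 24 |
| C | 24 / 48 | 67% | 36 / 36 |

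With SLS scored 0, 1, 2, its correlation with period is 0.45 now and 0 when balanced.

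**Precision in a period-adjusted model** (linear approximation, sequence fixed). Let d be the Period 2 minus Period 1 difference for a subject, V its variance and π the period effect. The three sequence means d1 (A-C), d2 (B-C) and d3 (C-B) each have variance V/24 and expectations (C-A)+π, (C-B)+π and (B-C)+π.

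- π is estimated by (d2+d3)/2, variance V/48.
- C-B is estimated by (d2-d3)/2, variance V/48.
- C-A is estimated by d1 minus the estimate of π: V/24 + V/48 = 1.5V/24.
- B-A is estimated by d1-d2: 2V/24.

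In the balanced layout, with d4 for C-A, the C-A contrast is (d1-d4)/2 with variance (V/12+V/12)/4 = V/24. B-A is V/24 + V/48 = 1.5V/24, and C-B stays V/48. The ratios are 1.5 for C-A and 2/1.5 = 1.33 for B-A. If between-subject information is also used, the C-A ratio is 1.29-1.43 for an assumed intra-subject correlation of 0 to 0.7.

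**Estimability.** Three sequences by two periods give six cell means. Intercept (1), treatment (2), period (1) and sequence (2) use all six. Additivity therefore cannot be tested, and the planned treatment-by-period term cannot be estimated beside sequence. The balanced layout has eight means and seven main-effect parameters, which leaves one interaction degree of freedom.

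**Bias without a period term.** The documents give no period effect, so these values are assumptions. Suppose there is no SLS effect and incidence is 20% in Period 1 and 40% in Period 2:

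- A: 20%
- B: (24×20 + 24×40)/48 = 30%
- C: (24×20 + 48×40)/72 = 33.3%

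At 25% then 40% the expected rates are 25%, 32.5% and 35%. Simulated two-sided Cochran-Armitage rejection with no SLS effect, over a range of within-subject dependence:

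| Period 1 to Period 2 | Current layout |
|---|---|
| 10-point rise (20% to 30%, 25% to 35%) | about 4-9% |
| 25% to 40% | 8-13% |
| 20% to 40% | 15-21% |

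For the two larger rises nearly all rejections are in the hypothesised direction, and the balanced layout gives about 2-5%. For a fall from 40% to 25%, about 11-14% reject, nearly all in the opposite direction (within-subject correlation 0 to 0.5).

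**Period-I-only fallback** (exact Fisher power, same convention). Group sizes change from 24/24/24 to A 12, B 24, C 36.

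| Comparison | Current | Balanced |
|---|---|---|
| B vs A, 25% vs 1% | 67% | 21% |
| C vs A, 50% vs 1% | 99.5% | 96% |
| C vs B, 50% vs 25% | 34% | 41% |

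**The case against.** The strongest reply is that the primary model already includes period. That stands. A reader might infer that A is wholly confounded with period and that the primary result is biased. It is not: B-C and C-B identify the period effect, and A's contrasts are estimable if effects are additive.

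A reader might also infer that every unadjusted analysis is biased. The Period-I-only Fisher test is not; it is a randomised parallel comparison, currently 24/24/24. The split weakens it for B vs A. That cost is real but limited, because the interaction that triggers this fallback cannot be estimated beside sequence in the current design.

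The size of the bias is assumed. A rejection rate near 20% needs a period shift of about 20 points; for a 5-point shift the test stays near nominal (2-6%). At the plan's own 1/25/50%, a small mixed-model simulation (150 runs) put A vs C power at about 99% in both layouts, so the precision loss matters mainly for smaller differences.

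The split also places half of A's exposures after high SLS, open to carry-over and to loss of subjects during C, with no replacement (Section 4.6) and no imputation (Section 9.6). This stands. The plan accepts the same order for B, and C-A subjects would have at least a week on A first, but A is the reference.

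Finally, stratifying by period removes the bias in the secondary tests without a new sequence. This is true, but it does not recover the lost precision or make any interaction estimable.

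**Conclusion.** The concern holds as partial confounding. In the primary model it costs precision (variance ratios 1.5 for C-A and 1.33 for B-A, from a linear approximation with fixed sequence) and forces reliance on untestable additivity. In the pooled Wilson rates, Cochran-Armitage test, all-data Fisher fallback and adverse-event Fisher tests it is a bias whose size and sign follow the unknown period effect: slight for a few points, material from about 15 points, and able to mask a true trend if incidence falls over time. The documents do not show that a period effect exists. The sponsor should make the change because it is cheap and protects the reference arm, not because the primary analysis is invalid.

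**What to change.** Randomise 12 subjects to A-C, 12 to C-A, 24 to B-C and 24 to C-B (1:1:2:2). Amend the sequence table in Section 3.1, the order statement in Section 5.1 and the ratio in Section 8.1, and regenerate Appendix II. N = 72, the 24/48/72 exposures, the product counts and the stated 74% and 77% are unchanged.

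The protocol should state the two costs: half of A's exposures follow C, and the Period-I-only fallback becomes 12/24/36 with the power shown above.

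If the three sequences are kept, stratify the Cochran-Armitage and Fisher tests by period, or test the trend inside the period-adjusted model, and report rates by toothpaste within period. In simulation a period-stratified trend test returned rejection to about 2-6%. This costs only analysis text.
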